### 2.2 Study Objectives

#### 2.2.1 Primary Study Objective

##### Stage 1

The primary objective of the study is to assess the safety of increasing doses of Dysport in vulvodynia subjects with PVD.

##### Stage 2

The primary objective of the study is to assess the efficacy of Dysport compared to placebo in vulvodynia subjects with PVD.

#### 2.2.2 Secondary Study Objectives

The secondary objectives of the study are as follows:

##### Stage 1

- To assess the efficacy of increasing doses of Dysport compared to placebo in vulvodynia subjects with PVD
- To determine the doses of Dysport to be administered in Stage 2
- To assess the sensitivity of the endpoints used in Stage 1.

##### Stage 2

- To define the optimal doses of Dysport with an acceptable benefit/risk profile for the treatment of vulvodynia with PVD
- To assess effect of Dysport on:
  - Vulvar pain
  - Use of pain rescue medication (type, dose and frequency)
- To determine if primary and secondary PVD subjects benefit from Dysport administration
- To assess the time to retreatment
- To assess the safety of Dysport.

### ***2.2.3 Exploratory Objectives***

The exploratory objectives of the study are as follows:

- To assess effect of Dysport on:
  - Clinical Global Impression (CGI) of the treatment effect (assessed by the investigator)
  - Patient Global Impression of severity of the pain (PGI-S) and Patient Global Impression of change in pain (PGI-C)
- Emotional response, cognitive response and associated life interference as assessed on modified Vulvar Pain Assessment Questionnaire (mVPAQ) subscales
- Sexual function
- To assess the efficacy of Dysport on the pelvic floor muscles pressure
- To assess the efficacy of Dysport on depression
- To assess the efficacy of Dysport on the quality of life.

### 3 STUDY DESIGN

#### 3.1 General Design and Study Schema

This is a Phase II multicentre, double-blind, randomised, placebo-controlled, dose finding study to define the optimal doses of Dysport and evaluate its efficacy and safety compared to placebo in vulvodynia patients with PVD. Study treatment will be injected at 5 needle insertion points at 10 injection sites in the vestibular area. The study will consist of a dose escalation stage (Stage 1) and a dose expansion stage (Stage 2). The purpose of the dose escalation will be to determine the Dysport doses to be further investigated in Stage 2. The study will include approximately 180 premenopausal female subjects (up to 118 in Stage 1 if all cohorts are reached, and 63 in Stage 2) aged 18 years or above with a diagnosis of PVD associated with provoked pain at the posterior vestibule. Both Stage 1 and Stage 2 will consist of a double-blind period (treatment cycle 1; Dysport or placebo) followed by an open-label treatment period (treatment cycles 2 to 4; all subjects receive Dysport). Overall study duration and period for individual subject participation are provided in Section 3.8.

An overview of the study design is presented in [Figure 1](#).

##### 3.1.1 Stage 1 (Dose Escalation)

It is intended to enrol up to seven dose level cohorts of secondary PVD subjects (i.e. having a past history of pain-free intercourse or insertion of any object >1 cm diameter; hereafter referred to as PVD2 subjects) evaluating Dysport doses ranging from 100 U up to a maximum of 800 U (total dose administered) to find two optimally safe and effective doses of Dysport that will be further investigated in the Stage 2. Additional dose level cohorts within this dose range (100 U and up to a maximum 800 U) may potentially be added based on the recommendations from the DRC.

Each PVD2 cohort will include 10 unique evaluable PVD2 subjects who will be randomised via the interactive response system (IRS) to the two double-blind parallel treatment arms in 4:1 ratio:

- Dysport (N=8) or
- Placebo (N=2).

Cohort 4 will include 8 unique evaluable primary PVD subjects (i.e. having life-long provoked vestibular pain; hereafter referred to as PVD1 subjects), at the same Dysport dose as for the PVD2 Cohort 3, who will be randomised via the IRT to the two double-blind parallel treatment arms in 3:1 ratio:

- Dysport (N=6) or
- Placebo (N=2).

Further PVD1 cohorts (i.e. above 400 U) will include 10 unique evaluable subjects randomised in a ratio of 4:1 (Dysport N=8 and Placebo N=2).

In an event, when the last subject in a cohort is being randomised, if an additional subject has been screened, this subject may be accepted in the cohort and be randomised.

At Screening, all subjects will be allocated a subject number. Subjects will be evaluated for eligibility during a Screening Visit at Day -14. Following confirmation of eligibility for the study, subjects will be allocated to one of the above two treatment groups. Subjects will receive study treatment injections in the pelvic floor muscles on Day 1 (Baseline Visit). Follow-up visits will be performed at:

- Week 2 (telephone contact)

- Week 6
- Week 12 and
- Every 6 weeks up to a maximum of 48 weeks of follow-up.

The screening and postbaseline assessments to be performed at each visit are discussed in Section 5.2. Assessments to be performed at the End of Study (EOS) or Early Withdrawal (EWD) visit are presented in Section 5.2.4.

Once all PVD2 and PVD1 evaluable subjects in a dose level have reached the Week 6 visit, the dose escalation for the subsequent cohort will be agreed at the DRC meeting upon review of the available efficacy and safety data. The maximum dose to which escalation is permitted will be 800 U. The definitions for clinically significant AEs and dose limiting events (DLEs) is provided in Section 3.1.1.1. The assessments to be performed by the Data Review Committee (DRC) and their timings are discussed in Section 3.1.1.2. Subject who withdraw or discontinue prior to Week 6 in the double-blind period for reasons unrelated to occurrence of DLEs may be replaced at the discretion of the investigator and sponsor. Replacement subjects will receive the same treatment as the subject they replace. Stage 1 will be stopped as soon as the dose of 800 U has been tested or otherwise recommended by the DRC.

At the end of Cycle 1 – Week 6 for all PVD2 subjects in Stage 1, the DRC will meet to review efficacy and safety data and recommend the two doses of Dysport to be assessed in the Stage 2 of the study. PVD1 subjects will be recruited in Stage 2 following DRC review of the efficacy and safety data of PVD1 cohort(s) in Stage 1.

An intermediate analysis will be performed to review the unblinded data from all cohorts in Stage 1 up to Cycle 1-Week 12 in an effort to select the two doses for Stage 2 taking into account the dosing recommendations from the DRC.

From Week 12 onwards of the double-blind period, subjects will be assessed for the need for retreatment at each visit. Subjects who require retreatment will be provided subsequent treatment with Dysport in the open-label period of the study. Dysport dose levels, that are approved by the DRC will be used for retreatment and will not exceed 800 U. Subjects not requiring or not eligible for retreatment will be evaluated every 6 weeks  $\pm 2$  weeks (Additional Visit(s)) until they need retreatment or they complete at least 36 weeks of follow-up. The number of treatment cycles will depend on the duration of each treatment cycle, and thus the minimum follow-up duration will be 36 weeks and the maximum follow-up duration will be 48 weeks (the end of the study will not occur before 12 weeks have elapsed from the last treatment cycle), as calculated from Cycle 1-Day 1.

The screening and postbaseline assessments to be performed at each visit are discussed in Section 5.2. Assessments to be performed at the EOS or EWD visit are presented in Section 5.2.4.

Retreatment criteria are presented in Section 3.7.3. Retreatment dose schedule for Stage 1 is presented in Section 3.7.2.1.

### *3.1.1.1 Definitions of Clinically Significant Adverse Event and Dose Limiting Event*

A clinically significant AE is defined as:

- Drug-related severe AE or drug related serious AE
- Treatment emergent faecal incontinence, defined as new onset faecal incontinence that lasts for more than 4 days and that in the investigator's opinion is not due to any other cause e.g. diarrhoea

- Treatment emergent urinary incontinence, defined as: new onset, or a significant and sudden deterioration in any pre-existing urinary incontinence in the investigator's opinion, that lasts for more than 4 days and that in the investigator's opinion is not due to any other cause.

A DLE for the purpose of this study is defined as a clinically significant AE that would preclude another drug administration at the same dose level in a given subject.

### 3.1.1.2 *DRC Meetings*

A DRC will be established to make recommendations for dose escalation, dose de-escalation, progression from Stage 1 to Stage 2 or study termination in Stage 1 of the clinical study (see Section 13.3.1 for the composition and operation of the DRC). The maximum dose to which escalation will be permitted will be 800 U.

If no subject reports a clinically significant AE in a cohort, the DRC will meet once all PVD2 and PVD1 evaluable subjects of a dose level have reached Week 6 to review the unblinded efficacy and safety data and recommend the dose for the next cohort. The DRC may recommend to reassess the previously used dose level based on the review of efficacy and safety data from the cohort(s).

If any subject reports a clinically significant AE (as defined in Section 3.1.1.1), then further enrolment into the cohort, as well as retreatment in open label cycles at current dose, will be suspended and an ad hoc DRC meeting will be scheduled.

During the ad-hoc meeting, the DRC will review blinded data of the subject(s) with clinically significant AE and all available efficacy and safety data from the cohort. The DRC may request to break the blind to confirm if the significant AE is a DLE, and based on this assessment, if enrolment in the cohort may continue.

At the end of Cycle 1-Week 6 visit for all subjects in Stage 1, the DRC will meet to review all safety and efficacy data from the cohort(s) and recommend the two doses to be assessed in Stage 2. The DRC will also recommend if further PVD1 cohort(s) are required or if PVD1 subjects should be removed from Stage 2.

In Stage 2 of the study, ad hoc DRC meetings will be scheduled to review efficacy and safety data in the event of an emergency safety issue.

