**Stage 1 (Dose Escalation) Double-Blind Period:**

It is intended to enrol up to seven dose level cohorts of secondary PVD subjects (i.e. having a past history of pain-free intercourse or insertion of any object >1 cm diameter; hereafter referred to as PVD2 subjects). Each cohort will include 10 unique evaluable PVD2 subjects. Subjects in these cohorts will be randomised in a ratio of 4:1 (Dysport: 8 + Placebo: 2) in a dose-escalation manner starting with a total Dysport dose of 100 U, then 300 U, and thereafter increasing up to a maximum of 800 U by increments of 100 U.

For Dysport doses equal to or above 400 U, cohorts of primary PVD subjects (i.e. having life-long provoked vestibular pain; hereafter referred to as PVD1 subjects), will be recruited in parallel with PVD2 cohorts and at the same Dysport dose as for the PVD2 cohorts. The first PVD1 cohort at 400 U will include eight unique evaluable subjects who will be randomised in a ratio of 3:1 (Dysport: 6 + Placebo: 2). Further PVD1 cohorts (i.e. above 400 U) will include 10 unique evaluable subjects randomised in a ratio of 4:1 (Dysport: 8 + Placebo 2).

The recommendation for dose escalation/de-escalation and the staggering scheme for the subsequent cohort will be agreed at data review committee (DRC) meetings upon review of efficacy and safety data from the previous cohort(s).

Subjects who discontinue prior to Week 6 for reasons unrelated to occurrence of dose limiting events (DLEs) may be replaced at the discretion of the investigator and sponsor. When all subjects in Stage 1 have completed 6 weeks of follow-up of treatment cycle 1, the DRC will meet again to enable selection of dose(s) to be assessed. PVD1 subjects will be recruited in Stage 2 based on the DRC review of efficacy and safety data obtained from PVD1 cohort(s) in Stage 1.

Following evaluation of study eligibility at the Screening Visit (Day -14), subjects will receive study treatment injections in the pelvic floor muscles on Day 1 (Baseline Visit). Follow-up visits will be performed at:

- Week 2 (telephone contact)
- Week 6
- Week 12 and
- Every 6 weeks up until eligible for retreatment or up to a maximum of 48 weeks of follow-up.

An intermediate analysis will be performed to review the unblinded data from all cohorts in Stage 1 up to Cycle 1-Week 12 in an effort to select the two doses for Stage 2 taking into account the dosing recommendations from the DRC.

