#### **Data Review Committee (DRC) Meetings:**

A DRC will be established to make recommendations for dose escalation and dose de-escalation (within the Dysport dose range of 100 U up to a maximum of 800 U) or study termination in Stage 1. If no subject reports a clinically significant AE in a cohort, the DRC will meet once all evaluable subjects have reached Week 6 of a cohort to review the efficacy and safety data and recommend the dose for the next cohort or proceed to Stage 2.

If any subject reports a clinically significant AE, then further enrolment into the cohort, as well as retreatment in open label cycles at the current dose, will be suspended and an ad hoc DRC meeting will be scheduled to review the safety data and make a recommendation with regards to further conduct of the cohort and of Stage 1. At the end of Cycle 1-Week 6 for all subjects in Stage 1, the DRC will meet to review efficacy and safety data and recommend the two doses of Dysport to be assessed in the Stage 2 of the study. The DRC will also recommend if further PWD1 cohort(s) are required or if PWD1 subjects should be removed from Stage 2.

In Stage 2 of the study, ad hoc DRC meetings will be scheduled to review efficacy and safety data in the event of an emergency safety issue.

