#### Double-Blind Period (Treatment Cycle 1)

The starting dose for PVD2 Cohort 1 will be Dysport 100 U or placebo. It is anticipated that if there are no safety issues, then the predefined doses for PVD2 Cohorts 2 and 3 will be 300 U and 400 U, respectively, and doses for Cohorts 5, 7, 9 and 11 will be 500 U up to a maximum of 800 U by increments of 100 U, all with matching placebos. Subjects in PVD1 Cohorts 4, 6, 8, 10 and 12 will receive the same dose as subjects in PVD2 Cohorts 3, 5, 7, 9 and 11. The DRC may recommend to reassess the previously used dose level based on the review of efficacy and safety data from the cohorts.

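### From 400 U upward, the automatic hold after a clinically significant AE stops enrolment only into 'the cohort', which can be read as leaving the paired cohort at the same dose open

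*Protocol*

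**What the plan says.** The synopsis (Stage 1 double-blind period) states that from 400 U PVD1 cohorts "will be recruited in parallel with PVD2 cohorts and at the same Dysport dose as for the PVD2 cohorts". Section 3.7.2.1 sets out the pairs: PVD1 Cohorts 4, 6, 8, 10 and 12 "will receive the same dose as subjects in PVD2 Cohorts 3, 5, 7, 9 and 11".

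The rule for a clinically significant AE appears twice in almost the same words. Section 3.1.1.2 has "then further enrolment into the cohort, as well as retreatment in open label cycles at current dose, will be suspended", and the DRC paragraph of the synopsis has "then further enrolment into the cohort, as well as retreatment in open label cycles at the current dose, will be suspended". In both, one sentence sets two holds with different scopes.

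Section 3.1.1.2 then has the ad hoc DRC look at the affected subject's blinded data and "all available efficacy and safety data from the cohort", and decide whether that cohort may go on enrolling. The synopsis is broader: the DRC reviews the safety data, with no cohort limit, and is to "make a recommendation with regards to further conduct of the cohort and of Stage 1".

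SAP section 1.3.5 repeats the rule with the same split in scope.

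**The concern.** This sentence is the only hold that starts by itself, before anyone has met or exercised judgement. Stage 1 is a dose escalation with safety as its primary objective. The published support cited in section 1.5 stops at 400 U, the dose at which paired recruitment begins.

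On the numbered-cohort reading, a qualifying event in Cohort 5, for example, stops Cohort 5 enrolment and all open-label retreatment at 500 U. Cohort 6 can still give women their first blinded injection at 500 U. The protocol gives no reason why pain-onset subtype should decide which of two groups at one dose is paused. A site or the IRT operator would have to choose a reading on the day of the event.

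**Working it through.** **Does the protocol count the pairs as separate cohorts?** The stated Stage 1 maximum is 118. Seven PVD2 cohorts of 10, one PVD1 cohort of 8 and four PVD1 cohorts of 10 give 7 × 10 + 8 + 4 × 10 = 118. The figure reproduces with twelve separate cohorts.

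**Usage supporting the numbered-cohort reading**
- Section 3.5: from Cohort 3 the IRT uses pain-onset subtype to assign the cohort, and recruitment closes cohort by cohort, at 10 (8 in Cohort 4).
- Section 4.1, inclusion criterion 12b: from Cohort 3 onward, odd-numbered cohorts take secondary and even-numbered cohorts primary vulvodynia.
- Section 3.1.1.2, no-event branch: where both subtypes are plainly meant, the text says dose level ("the DRC will meet once all PVD2 and PVD1 evaluable subjects of a dose level have reached Week 6").
- The hold sentence itself uses dose as the scope of one hold and cohort as the scope of the other.

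**Usage supporting the dose-level reading**
- The same no-event sentence goes on to speak of the dose for the next cohort, which from 400 U means the next pair.
- Section 3.1.1 has the subjects in a dose level reach Week 6 and then refers to escalation for the subsequent cohort.
- Section 11.2 speaks of no DLEs in a cohort with 16 active subjects, which is a pair. The matching synopsis sentence says two cohorts.
- Section 3.7.2.1 (open-label period) uses the following cohort to mean the next dose.

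Neither list settles the matter, and no section defines the term.

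**Ceiling on further active first doses, numbered-cohort reading.** The inputs are the planned sizes in the synopsis and section 3.1.1.

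| Event in | Cohort left open | Planned (active + placebo) | Ceiling |
|---|---|---|---|
| Cohort 3 (400 U) | Cohort 4 | 6 + 2 | 6 |
| Cohort 4 (400 U) | Cohort 3 | 8 + 2 | 8 |
| Either cohort at 500 to 800 U | its partner | 8 + 2 | 8 |

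At 100 U and 300 U there is one cohort per dose, so the question does not arise. Each further enrolment carries an expected 6/8 = 0.75 active exposures in Cohort 4 and 8/10 = 0.80 elsewhere. The ceiling supposes that the open cohort is empty at the event and fills before the DRC meets. It leaves out replacements and the one extra screened subject that section 3.1.1 allows. Under a dose-level hold the number is 0.

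**Open-label events.** The trigger is not limited to cycle 1. Under section 3.7.2.1 a subject may be retreated at her cohort's dose or at the next approved dose, and the note to Figure 1 keeps her in her original cohort to the end of study. Two cases follow.
- A Cohort 3 subject has an event after open-label 500 U. Her cohort is a 400 U cohort, so neither reading of her cohort clearly stops first dosing at 500 U.
- A Cohort 2 subject has an event after open-label 300 U while Cohorts 3 and 4 enrol at 400 U. Enrolment at 300 U would usually be complete by then, so a hold at that level alone would stop nothing while a higher dose went on enrolling.

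**The case against.** The strongest reply is that the event branch is the complement of the no-event branch, where the cohort is resolved by the whole dose level, so a sensible reader would carry that meaning over. This stands as far as it goes: it makes the text ambiguous. It does not explain why the same sentence scopes the other hold by dose.

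Second, other safeguards exist. The DRC can advise on all of Stage 1 (synopsis). The DRC may recommend stopping a cohort or the study, and the sponsor may stop either at any time (section 3.9). Safety data are monitored continuously (8.1), SAEs are reported within 24 hours (8.1.6), and "the staggering scheme for the subsequent cohort will be agreed at data review committee (DRC) meetings". These are real and would probably shorten any gap. All need a meeting, an agreement or a judgement, so none replaces an automatic hold.

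Third, the DRC charter (13.3.1; SAP 1.3.5) may define the hold. That cannot be checked here.

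Fourth, little was at stake in the event. SAP section 1.3.5 reports that the study closed after Cohorts 1 to 6, so only the 400 U and 500 U pairs were reached, and that the DRC noted no safety concerns. This limits the practical consequence but leaves the wording as it is.

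A reader might also infer that the ad hoc DRC is barred from seeing the partner cohort's data. The documents do not support that: section 3.1.1.2 lists what will be reviewed without excluding anything else, and the synopsis sets no cohort limit.

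**Conclusion.** The point holds as an ambiguity in a safety rule. Followed literally, with the cohort taken as the numbered one, the one automatic hold stops repeat dosing at the affected dose but not first blinded dosing in the paired cohort. The size is a ceiling of 6 active exposures (Cohort 4 open) or 8 (any other paired cohort open), resting on planned cohort sizes and on an empty partner that fills before the DRC meets. The real number would be lower, since a qualifying event in the partner would suspend that cohort too and enrolment may be staggered.

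Two stronger conclusions are tempting. One is that the protocol plainly allows the partner to continue. It does not say so, and several sections use cohort for a dose level. The other is that an expected number of extra exposures, or of further DLEs, can be calculated. A pace averaged from document dates would mix in the 100 U and 300 U periods, when only one cohort recruited, and would rest on an assumed first enrolment and an assumed time to the meeting. A DLE probability would need a DLE rate, which the documents do not give.

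This is a cheap improvement; confidence is medium because the charter is unseen.

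**What to change.** In section 3.1.1.2 and the DRC paragraph of the synopsis, replace the enrolment clause with: *further enrolment into all cohorts (PVD1 and PVD2) at the dose level assigned to the subject's cohort or, for an event in an open-label cycle, at the open-label dose she received, and at any higher dose level then enrolling*. State that this applies whatever the blinded allocation, which is not known when the hold starts.

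In section 3.1.1.2, have the ad hoc DRC review all available data at the affected dose level or levels, and make its decision on resuming enrolment apply to the same levels. The SAP needs no change: section 1.3.5 only recounts the rule, and the study has closed.

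The cost is a few words in two places and an IRT setting. The downside is a short pause in the parallel or higher-dose cohorts, sometimes for an event that proves to be on placebo or not a DLE.

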### 3.1.2 *Stage 2 (Dose Expansion)*

Two dose levels identified from Stage 1, recommended by the DRC based on efficacy and safety data, will be investigated further and compared to placebo in Stage 2. As for Stage 1, 800 U will be the maximum permitted dose in Stage 2. It is intended to enrol 63 subjects in the randomisation ratio of 1:1:1:

- Dysport high dose (optimal highest safe and efficacious dose): 21 subjects
- Dysport low dose (selected based on safety and efficacy considerations observed in Stage 1): 21 subjects, and
- Placebo: 21 subjects.

Following the review of data available from Stage 1, the sample size may be formally recalculated for Stage 2 after the intermediate analysis.

[figure not shown]
Subjects will be evaluated for eligibility during a Screening Visit at Day -14. Subjects will receive study treatment in the pelvic floor muscles on Day 1. Treatment paradigm and follow-up visits will be the same as in Stage 1. From Week 12 visit onwards, the need for retreatment will be assessed at each visit.

[figure not shown]
The screening and postbaseline assessments to be performed at each visit are discussed in Section 5.2.

Retreatment criteria are presented in Section 3.7.3. Retreatment dose for Stage 2 is presented in Section 3.7.2.2.

The number of treatment cycles will depend on the duration of each treatment cycle, and thus the minimum follow-up duration will be 36 weeks and the maximum follow-up duration will be 48 weeks (the end of the study will not occur before 12 weeks have elapsed from the last treatment cycle), as calculated from Cycle 1-Day 1.

Figure 1 Study Design

Each subject included in a cohort is unique and will continue to remain in the same cohort until the EOS.

